6. ASSESSMENT AND FOLLOW UP

Women will be assessed by the researchers at four different visits. At the first antenatal visit, the general care team will mention the study, if the patient consents, she will then be approached by the researchers to explain the study protocol. At the second visit, when the OGTT is performed, women who decided to take part in the study will sign the consent form. At the next antenatal visit where results from the OGTT are explained, women included will be randomised. The last research visit will take place at 28 weeks gestation. Additionally, they will be contacted weekly, by telephone to assess compliance and confirm willingness to participate in the study. All participating women will continue to attend routine follow up by the Obstetrics team at the antenatal clinic. Women diagnosed with GDM in early pregnancy will continue their routine care under the Obstetric team at Queen Charlotte's Hospital. We will be collecting information regarding treatment from the notes taken at this follow-up visits.

1st visit (≤16 weeks gestation)

Women with a previous history of GDM will be considered at high risk of recurrence and will be referred to the antenatal clinic before 16 weeks of pregnancy. At this first visit, the direct care team will inform them about the study and ask them if they are willing to speak with a member of the research team. If they agree, a research team member will explain the protocol and invite them to participate in the study. An information sheet will be provided and women will have time to consider if they are willing to participate and inform the research team at their next antenatal visit.

2nd visit

Women who decide to participate will inform the research team when they attend their second antenatal visit, when an OGTT is to be performed. In this visit, women willing to participate will be asked to sign a consent form.

As part of the standard pregnancy care, these women will be booked for GDM early screening. The following investigations will be performed as part of their usual NHS care:

- Blood tests: full blood count, renal function. GAD antibodies can be requested in women in whom type 1 diabetes is suspected.
- Urine sample to test for proteinuria, glycosuria, leucocytes and nitrates.

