7. PARTICIPANT ENTRY

PRE-RANDOMISATION EVALUATIONS

Women will be evaluated by the mid-wife at the first visit in the antenatal clinic. An OGTT will be booked to test for early GDM in women with previous GDM considered at high risk of recurrence. Personal and medical history will be recorded. When women attend for the OGTT, blood and urine samples will be collected at 0 and 120 minutes.

INCLUSION CRITERIA

- Women with a history of GDM in previous pregnancies
- Age \geq 18 years
- Singleton pregnancy
- \leq 16 weeks gestation

EXCLUSION CRITERIA

- Women unable or unwilling to give consent
- Pre-gestational diabetes or use of anti-diabetic medication in the first visit
- Significant chronic medical conditions (cardiovascular, liver or kidney disease)
- Women participating in other medical trial
- Women who have undergone bariatric surgery
- Women with milk allergy/intolerance
- Women unable to speak/understand English

WITHDRAWAL CRITERIA

Participants will be free to withdraw at any time and are not required to give a reason.

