8. ADVERSE EVENTS

Adverse Event (AE): Any untoward medical occurrence in a patient or clinical study subject.

Serious Adverse Event (SAE): Any untoward and unexpected medical occurrence that: results in death, is life-threatening, requires hospitalisation, results in persistent or significant disability or incapacity or a congenital abnormality or birth defect

Medical judgement should be exercised in deciding whether an AE is serious in other situations. Important AEs that are not immediately life threatening or do not result in death or hospitalisation but may jeopardise the subject or may require intervention to prevent one of the other outcomes listed in the definition above, should also be considered serious.

REPORTING PROCEDURES

All adverse events should be reported. Depending on the nature of the event the reporting procedures below should be followed. Any questions concerning adverse event reporting should be directed to the Chief Investigator in the first instance.

Non serious AEs

All such events, whether expected or not, should be recorded.

Serious AEs

An SAE form should be completed and faxed to the Chief Investigator within 24 hours. However, relapse, death and hospitalisations for elective treatment of a pre-existing condition do not need reporting as SAEs. All SAEs should be reported to the sponsor.

All SAEs should be reported to the Bromley Research Ethics Committee where in the opinion of the Chief Investigator the event was:

‘Related’, i.e. resulted from the administration of any of the research procedures; and

‘Unexpected’, i.e. an event that is not listed in the protocol as an expected occurrence.

Reports of related and unexpected SAEs should be submitted within 15 days of the Chief Investigator becoming aware of the event, using the NRES SAE form for non-IMP studies.

Local investigators should report any SAEs as required by their Local Research Ethics Committee and/ or Research and Development Office.

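### The SAE section contradicts itself: its reporting rule exempts death, which its definition makes serious, and undefined or missing terms let some other serious events, including some GDM-related ones, miss the SAE route

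*Combined protocol and SAP*

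**What the plan says.** Everything at issue is in section 8 (Adverse Events) of the combined protocol and SAP.

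- **Definition.** An SAE is "Any untoward and unexpected medical occurrence that: results in death, is life-threatening, requires hospitalisation, results in persistent or significant disability or incapacity". Birth defects and congenital abnormalities are also on the list.
- **Judgement clause.** The section also asks for medical judgement on other events: "Important AEs that are not immediately life threatening or do not result in death or hospitalisation but may jeopardise the subject", or that may need intervention to prevent a listed outcome, should be treated as serious too.
- **Reporting route.** SAEs go on a form to the Chief Investigator within 24 hours, and all SAEs go to the sponsor. Those judged related and unexpected also go to the ethics committee.
- **Exemption.** Immediately after the 24-hour rule the text says that relapse, death and "hospitalisations for elective treatment of a pre-existing condition do not need reporting as SAEs".
- **General rule.** "All adverse events should be reported" stands at the head of the reporting procedures. Non-serious events need only be recorded.

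Two statements elsewhere bear on how the exemption is read. Section 7 enrols "Women with a history of GDM in previous pregnancies". Section 6 says: "Women with a previous history of GDM will be considered at high risk of recurrence".

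**The concern.** A site following the exemption as written could leave a death off the SAE form, although death is the first criterion in the definition. That conflict needs no interpretation. The other terms are a problem because they are open. *Relapse*, *pre-existing* and *unexpected* each need a meaning or a reference point that the protocol does not supply, and a stay that is lengthened is not listed at all.

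What is at stake is safety oversight. The 24-hour form and the sponsor report attach only to SAEs. No other planned data item fills the gap. In the early GDM cohort the outcome data are need for insulin, days to insulin and dose. In the glucose tolerant cohort the endpoint is GDM yes or no. Neither records whether a woman was admitted. Section 9 also states that researchers are not blinded, so staff who know the allocation may be the ones deciding how the open terms apply.

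**Working it through.** The plan gives no figure on this point and no arithmetic applies. The check sets the definition against the exemption, item by item.

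1. **Death.** Definition: serious. Exemption: no SAE report needed. The two conflict directly. Grammatically, the qualifier about elective treatment attaches to hospitalisations and not to death. Even if the phrase about a pre-existing condition were stretched to cover death, some deaths would still be exempt. The later instruction that all SAEs go to the sponsor does not settle the matter: it could be read to bring deaths back in, or to apply only to what remains after the exemption.

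2. **Relapse.** The word occurs nowhere else in the document. Sections 4, 6 and 7 call the return of GDM *recurrence*. Still, the only recurring condition common to all participants is GDM, since section 7 requires previous GDM. Recurrent GDM is therefore a plausible reading, and it is the glucose tolerant cohort's endpoint (sections 3, 6 and 9). The exemption has no severity limit, so on that reading an admission caused by the recurrence could be left off the form. That last step is a further inference.

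3. **Elective admission for a pre-existing condition.** No date is given against which *pre-existing* is judged.
   - Early GDM cohort: GDM is diagnosed from the OGTT before randomisation (section 6, 3rd visit). A planned admission for GDM can be read as exempt.
   - Glucose tolerant cohort: GDM arising after randomisation is not pre-existing, and section 7 excludes diabetes that predates pregnancy. This clause does not reach those women's GDM.
   - Either cohort: an unplanned admission is not elective, so this clause does not exempt it.

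4. **Unexpected.** The definition requires it. The only explanation comes later, in the ethics committee test, where unexpected means not listed in the protocol as an expected occurrence. The protocol contains no such list. Two readings follow:
   - If that explanation also governs the definition, every event is unexpected and the word excludes nothing.
   - If the word has its ordinary meaning, a serious event that staff anticipated is not an SAE at all. In women whom section 6 already treats as likely to have a recurrence, that could include GDM-related events.

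5. **Prolonged hospitalisation.** The definition covers an event that "results in death, is life-threatening, requires hospitalisation, results in persistent or significant disability or incapacity". An event that lengthens a stay already under way meets none of these unless it is also life-threatening, disabling or similar. It then depends on the judgement clause, which can cover it but does not name it.

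6. **What remains reportable.** An unplanned GDM admission that is not classed as a relapse and is unexpected meets the hospitalisation criterion, and no exemption applies. The general rule on reporting all adverse events covers every case above, but it states no recipient and no deadline.

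**The case against.** The strongest reply is that the section has its own safeguards. All adverse events are to be reported, and the judgement clause says that important events should be considered serious. GDM diagnosis and insulin use are captured as outcomes, so worsening glycaemia does not go unseen. *Relapse* may be template wording that was never adapted, and exempting a recurrence of GDM as such does no harm, because a diagnosis alone should not be an SAE.

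Much of this stands. It makes prolonged hospitalisation a lesser gap, and it means that recurrent GDM is one reading of *relapse* and not the only one. It does not answer the exemption of death. Nor does a general rule without recipient or deadline replace the 24-hour form, and outcome data on insulin or diagnosis do not record admissions.

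A reader might infer more than the text supports:

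- **That any GDM-related admission is exempt.** It is not, for the reasons in steps 3 and 6 of the working.
- **That a between-arm SAE comparison would be distorted.** Section 9 plans no safety analysis. The effect is on oversight and on any later safety summary.
- **That the cited recurrence rate of over 40% measures the problem.** It is a rate of recurrence, not of admission, and it is not specific to women who pass early screening.
- **That one missed event is 5% of an arm.** Forty women in two arms would give 20 each, and 1/20 = 5%. But the two cohorts are randomised and compared separately, and their sizes are not given, so 20 is not the size of any planned comparison group.

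**Conclusion.** The point holds in this limited form. Section 8 contradicts itself on death, and that conclusion rests on the text alone. The remaining routes by which a serious event could escape SAE reporting are conditional:

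- *relapse*, if read as recurrent GDM;
- elective admission, if GDM diagnosed at the early OGTT counts as pre-existing;
- *unexpected*, if taken in its ordinary sense;
- a prolonged stay, if the judgement clause is not applied.

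The size cannot be estimated. The documents give no rate of death, admission or prolonged stay, and no figure in them can stand in for one. The efficacy analyses are unaffected. The section should be corrected because a death rule that contradicts its own definition should not be left to each reader, and because the correction is small.

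**What to change.** Revise section 8 in one amendment:

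1. Delete *death* and *relapse* from the exemption, so that it agrees with the definition. Deleting *relapse* alone would leave the main contradiction in place.
2. Limit the elective exemption to admissions planned before consent for a condition other than GDM.
3. Remove *unexpected* from the SAE definition and keep it only as part of the test for reporting to the ethics committee.
4. Add prolongation of an existing hospitalisation to the seriousness criteria.
5. State that a GDM diagnosis or the start of insulin, on its own, is a trial outcome and not an SAE, but that any event meeting a seriousness criterion is reported even when GDM is the cause.

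The cost is a one-paragraph protocol change and probably a few more SAE forms. Item 5 limits that burden by keeping the trial's own endpoints out of SAE reporting. Treatment and visits do not change.

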9. STATISTICS AND DATA ANALYSIS

Data handling and analysis will be carried out by SPSS version 20.0 version.

No power calculation to decide sample size will be used. The number of participants has been arbitrarily defined, as it is a pilot study. We aim to recruit 40 women.

Before randomisation, women will be categorised according to their glycaemic status in two cohorts: Glucose tolerant and GDM. Each of these two cohorts will be randomly allocated into the

intervention (soluble fibre supplement) and control (placebo) group. Randomisation will be by sealed envelopes. Participants but not researchers will be blinded as to the type of intervention prescribed.

Differences between group in each cohort will be assessed using Student t test or Mann-Whitney U test for numeric variables depending on distribution; χ^2 will be used for categorical variables.

In the Glucose tolerant women cohort:

For the primary outcome, GDM (yes/no), logistic regression analysis will be performed.

For the secondary outcomes, insulin sensitivity and insulin secretion, linear regression analysis will be performed.

In the early GDM cohort:

For the primary outcome, need for insulin treatment (yes/no), logistic regression analysis will be performed. Additionally days-to-treatment analysis will be performed for those participants starting insulin therapy during follow up.

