5. RANDOMISED CONTROLLED STUDY

Aim: To evaluate the effect of a soluble fibre supplement in glucose metabolism in pregnant women at high risk of developing gestational diabetes.

Study methodology: 12 week randomised, placebo-controlled, single-blinded study.

Intervention: Women will first be categorised according to their glycaemic status into two groups: GDM and glucose tolerant women. Afterwards, each group will be randomised into two groups and given either

- 1) Fibre supplement (Guar gum)
- 2) Placebo (Cellulose)

The participants will take the dietary supplement three times a day for 12 weeks. They will receive regular antenatal control according to NICE guidelines recommendations. Compliance will be addressed by weekly phone calls.

Number of volunteers: The number of participants will be arbitrarily define as no data of this type of intervention exists in this cohort. 40 participants will be recruited. Previous studies, outside pregnancy, have observed metabolic effects in samples of 15-40 subjects.

Recruitment: Women will be recruited in the antenatal clinic at Queen Charlotte and Chelsea's Hospital. An information sheet will be provided to eligible women in the first antenatal visit to explain the purposes of the study. Women who decide to take part will be asked to sign a consent form.

Randomisation: Initially women will be categorised according to glycaemic status in two cohorts: **Glucose tolerant** and **Early gestational diabetes (GDM)** cohort. Each of the two cohorts will then be independently randomised to either intervention or standard care using the sealed envelope website. Guar gum (intervention) and cellulose (placebo) will be provided in identical packed sachets.

STUDY OUTCOME MEASURES

PRIMARY OUTCOME MEASURES

- Glucose values at 0 and 120 minutes during an OGTT performed at 28 weeks in the glucose tolerant group.
- Glycaemic control assessed by need of insulin treatment (yes/no), days to insulin treatment and total insulin dose.

SECONDARY OUTCOME MEASURES

Assessing insulin sensitivity and insulin secretion at 28 weeks of pregnancy in the glucose tolerant cohort of women through validated indices using glucose and insulin (or C-peptide) values derived from the OGTT.

- Insulin sensitivity will be assessed using the Matsuda formula (18).
- Insulin secretion will be assessed by second-void fasting UCPCR as described by McDonald et al (19).

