- Women from the **Glucose tolerant cohort** will undergo a second OGTT. Blood and urine samples will be collected at 0 and 120 minutes. Glycaemic status will then be assessed with the endpoint being the diagnosis of GDM (yes/no). Insulin sensitivity and insulin secretion will be estimated using the same parameters as in the first visit. As part of the study, women will be weight to calculate BMI and gestational weight gain at 28 weeks gestation. The research team will have their last face to face visit with the participant to discontinue the intervention and answer any potential questions about the study.
- In women in the **Early GDM cohort**, glycaemic control will be assessed by the need of insulin treatment (yes/no) and in those requiring insulin the days-to-treatment (insulin) and total insulin dose will be recorded. Data will be obtained by reviewing medical records. As part of the study, women will be weight to calculate BMI and gestational weight gain at 28 weeks gestation. The research team will have their last face to face visit with the participant to discontinue the intervention and answer any potential questions about the study.

PROCEDURES

Women will be advised to fast for 10 hours the night before the oral glucose tolerance test. They will also be advised not to restrict carbohydrate ingestion the three days prior to the OGTT. At the antenatal clinic, blood samples will be collected at baseline (0 min) and at 120 min after the administration of an oral load of 75 g of glucose.

In the baseline sample other parameters will also be determined. Creatinine and HbA1c will measure in all participants and GAD antibodies will be requested in women in whom type 1 diabetes is suspected.

Serum insulin and C-peptide will be collected at 0 and 120 min during the OGTT.

Women will be advised to void their first urine before attending the antenatal clinic. Second-void fasting urine sample will be collected at 0 min during the OGTT. A second urine sample will be collected at 120 min. Urinary C-peptide will measure in these samples will be transfer to boric acid containers, the aliquoted into 1 ml cryotubes and stored at -80 °C until analysis. Serum creatinine will be collected at baseline (0 min) and measure in the central lab. The urinary C-peptide creatinine ratio (UCPCR) will be calculated using these data.

ASSESSMENTS

(i) Gestational diabetes

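### Researchers are left unblinded without a stated reason, and no masked caller, extractor or treating team is described for the early GDM cohort's insulin outcome

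*Combined protocol and SAP*

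**What the plan says.** Section 5 describes a "12 week randomised, placebo-controlled, single-blinded study", and the Study Summary also calls the design single-blinded. Section 9 says who is blinded: "Participants but not researchers will be blinded as to the type of intervention prescribed".

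On the products, Section 5 says: "Guar gum (intervention) and cellulose (placebo) will be provided in identical packed sachets". On allocation, Section 5 has each cohort "independently randomised to either intervention or standard care using the sealed envelope website", while Section 9 says "Randomisation will be by sealed envelopes".

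On contact with participants, Section 6 has the researchers assess women at four visits, one of which is the randomisation visit. It adds that "they will be contacted weekly, by telephone to assess compliance and confirm willingness to participate in the study". The caller is not named.

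On the early GDM outcome, the Study Summary and Section 9 make need for insulin (yes/no) the primary outcome, to be analysed by logistic regression. Section 5 lists days to insulin and insulin dose with it. For all of these, Section 6 (4th visit) says: "Data will be obtained by reviewing medical records". Section 6 also says, in the first person plural, that the study team collects treatment information from the follow-up notes. Routine care stays with the obstetric team. Section 10 lets the clinician depart from the protocol treatment at any stage.

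**The concern.** Starting insulin is a clinician's decision, not a laboratory reading, and the documents give no study criterion for it. Three routes are open by which knowledge of the arm could affect the comparison:

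- The weekly compliance contact may be conducted differently by arm.
- The arm may become known to the clinicians who decide on insulin.
- Whoever reads the notes may exercise judgement with the arm in view. This applies mainly to days-to-insulin and dose.

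The plan closes none of these routes, although the identical packaging and the web service would make most of that possible. At stake is whether a difference in insulin use reflects the supplement or awareness of it. Pilot status does not remove the problem, because an estimate distorted in this way would be carried into the planning of any later trial.

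**Working it through.** **No figure to reproduce.** Section 9 declares the 40 participants arbitrary, with no power calculation, and nothing numerical in the plan depends on blinding. The first check is of the text; the second is an illustration.

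**Step 1: what the text settles, task by task.**

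| Task | Who does it | Masked? |
|---|---|---|
| Taking the supplement | Participant | Yes (Section 9) |
| Study visits, including randomisation | Researchers (Section 6) | No (Section 9) |
| Weekly calls | Not named; listed with the researchers' visits (Section 6) | No masking described |
| Deciding on insulin | Obstetric team, in routine care (Section 6) | Not stated |
| Extracting insulin data | Study team (Section 6) | No masking described |
| 28-week OGTT, glucose tolerant cohort | Laboratory glucose against numerical cut-offs (Section 6, Assessments) | Much less exposed |

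That researchers make the calls and extract the data is an inference from Section 6.

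**Step 2: weight of one case.** The cohort split is not given. Assume 8 to 24 of the 40 women have early GDM, allocated 1:1, so n = 4 to 12 per arm. One woman handled differently moves her arm's insulin rate by 100/n percentage points: 100/4 = 25, 100/10 = 10, 100/12 = 8.3.

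**Step 3: effect on the comparison when the supplement does nothing.** Assume 10 per arm and a true insulin rate p in both arms. Let a fraction b of insulin starts in the guar gum arm be avoided or not recorded because the arm is known. The observed rate there is p(1 − b), and the spurious risk difference is p × b. The spurious odds ratio is [p(1 − b)/(1 − p(1 − b))] / [p/(1 − p)]. Rejection rates come from summing the exact binomial probabilities of all 10 v 10 tables that reach two-sided p < 0.05 (uncorrected chi-square, or Fisher).

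| p | b | Guar gum rate | Spurious difference | Odds ratio | Chi-square | Fisher |
|---|---|---|---|---|---|---|
| 50% | 0 | 50% | 0 | 1.00 | 4.2% | 1.3% |
| 50% | 20% | 40% | 10 points | (0.40/0.60)/1 = 0.67 | 6.2% | 2.2% |
| 50% | 40% | 30% | 20 points | (0.30/0.70)/1 = 0.43 | 12.8% | 5.5% |
| 30% | 0 | 30% | 0 | 1.00 | 3.7% | 1.2% |
| 30% | 20% | 24% | 6 points | (0.24/0.76)/(0.30/0.70) = 0.74 | 4.4% | 1.5% |
| 30% | 40% | 18% | 12 points | (0.18/0.82)/(0.30/0.70) = 0.51 | 6.9% | 2.5% |

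The planned primary analysis is logistic regression. The unadjusted Wald test at p = 50% rejects 3.9%, 5.6% and 10.3% of the time for b = 0, 20% and 40%.

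The result also varies with the split. At p = 50% and b = 40%, chi-square rejection rises from 7.0% to 10.8% with 4 per arm, and from 6.4% to 19.0% with 12 per arm. At p = 30% and 4 per arm it hardly changes (4.7% to 4.6%).

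**The case against.** Single-blinding is declared openly and consistently, in a 40-woman pilot. That stands: this is a weakness of design, not a contradiction or a concealed error.

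The route to bias is also indirect. Insulin is prescribed in routine care, and whether and when it was prescribed is a fairly objective reading of the notes. Participants are blinded, so they should not be able to tell the clinic their arm. This too stands in large part. It makes the calls and any disclosure to clinicians the stronger routes, and extraction of yes/no the weakest.

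The illustration assumes the bias whose effect it shows. A 40% loss means that awareness alone removes two insulin starts in every five, and milder cases move the rejection rate little. That is right, so the table shows sensitivity and predicts nothing.

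A reader might infer more than the documents support, in three ways:

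- *That the same individuals randomise, telephone and extract.* The text on randomisation and calls is in the passive, and no one is assigned to all three tasks.
- *That physical envelopes are opened by staff who can predict the next arm.* Section 9's wording may be shorthand for the website named in Section 5. Prediction from past allocations would need some restriction such as balanced blocks, and the documents mention none.
- *That the treating team knows the arm.* The documents are silent, which is a gap and not evidence of unblinding.

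**Conclusion.** The point holds as an avoidable weakness in the early GDM cohort. Researchers are expressly unblinded, no reason is given, and no safeguard is described for the calls, the insulin decision or the extraction. The glucose tolerant cohort's laboratory outcome is much less exposed.

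The part of the size that depends least on assumption is Step 2: in arms this small, a single case carries 8 to 25 points of the insulin rate. The rejection rates rest on an assumed 10 per arm, an assumed insulin rate and an assumed loss of starts in one arm. Quoting only the rise from 4.2% to 12.8% would mislead, because other equally arguable inputs give 6.2%, 6.9% or 4.4%. The documents do not support a claim that the result will be biased. They support a claim that the plan could not rule it out.

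**What to change.** In Section 9, replace the sentence that blinds participants only. State that participants, those who make the weekly calls, those who extract the insulin data and the treating obstetric team are all blinded. Bring the single-blind descriptions in the Study Summary and Section 5 into line.

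To carry this out, label the sachets by code number and have the website return only a code number. Hold the code list outside the study team until database lock, with an emergency code-break.

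Two facts need confirming first. The documents describe identical packaging but do not say that the opened contents look alike, and they do not show that the supplier can label by code. If either fails, the minimum is to mask the callers, extractors and treating team, using existing staff.

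Reconcile Sections 5 and 9 to one allocation method, the website. In the same edit, correct Section 5's description of the comparator as standard care, since it is placebo elsewhere.

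The cost is a protocol amendment and labelling logistics. The sample size does not change, and no participant needs an extra visit or procedure.
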